MAR imputations will be performed separately for each treatment arm and the imputation model will include terms for age at baseline, baseline SE (average of both eyes), and SE values (average of both eyes) for each post baseline scheduled visit through the specified analysis timepoint, Month 24 or Month 36 as applicable.

Imputations for data assumed to be MNAR will be first imputed via MCMC multichain methods to obtain monotone data as above for MAR imputations. The remaining missing SE values will be imputed via a sequential vehicle-based pattern imputation using regression methods (Ratitch, 2011) for the scheduled SE visits through the analysis timepoint, Month 24 or Month 36, using a model including age at baseline and baseline SE (average of both eyes) followed by sequential visits through M24 or M36, imputed values for those on SYD-101 treatment will be based on the Vehicle group.

EMA Submission:

The annual progression rate of myopia for a given timepoint will be calculated as the negative change in SE (average of both eyes) from baseline, divided by the number of days to the timepoint (visit date – date of first dose of study drug + 1), and multiplied by 365.25 days/year. The average of SE for the right and left eyes will be used for analysis.

SYD-101 0.01% and SYD-101 0.03% will be compared to Vehicle for the annual progression rate of myopia after 24 months of treatment using a REML-based MMRM model including fixed effects for treatment group, baseline age category, categorical visit, and the treatment group by visit interaction, with baseline SE value (average of both eyes) as a covariate. An appropriate covariance structure will be selected, and the Kenward-Roger Method will be used to calculate the denominator degrees of freedom for the test of fixed effects. All visits through Month 24 will be included in the model, with the primary comparison at the Month 24 visit.

The MMRM model will be repeated for each imputation and the results combined via SAS PROC MIANALYZE for final treatment estimates. The mean annual progression rate of myopia for each treatment and the estimated mean difference between each SYD-101 treatment group and Vehicle will be presented along with their corresponding 95% CIs.

The analysis of the primary endpoint will be based on the FAS. As a sensitivity analysis, an analysis will be repeated for the Per-Protocol Analysis Set and using other imputation approaches for the FAS.

US FDA Submission:

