4.1. Sample Size

Group sample sizes of 280 in each treatment arm will achieve at least 90% power to detect a difference in the percentage of participants with myopic progression (>0.75 D) of at least 15% between a SYD-101 arm and Vehicle. Power calculations presented in Figure 4-1 are based on the Chi-squared test at a 2-sided significance level of 0.025.

[figure not shown]
Figure 4-1 Power for 2-Sided Chi-Square Test Evaluated at Alpha=0.025 for Proportion Responders When 280 Participants Per Arm

Additionally, group sample sizes of 280 per treatment arm achieves >90% power to detect a reduction of 0.18 D or more in the annual progression rate between SYD-101 and Vehicle, assuming a common SD of 0.60 D. Power calculations presented in

Figure 4-2 are based on a 2-sample t-test evaluated at the 0.025 significance level.

Figure 4-2 Power for 2-Sided T-Test Evaluated at Alpha=0.025 for Annual Progression Rate When 280 Participants Per Arm

Furthermore, to estimate the statistical power of the two region- specific primary endpoints, simulations based on various assumptions regarding the mean vehicle annual progression rate, the mean active annual progression rate based on % reduction from the vehicle annual progression rate, the SD for the APR as well as allowing for participant dropout/study treatment discontinuation and escape medication have been considered to investigate statistical power for a range of sample sizes. Simulations were run after the protocol was finalized to assess protocol sample size assumptions. For the most likely assumption of parameters examined, a mean placebo/control APR of 0.65 D and a mean active APR 0.325 D (a 50% reduction from the mean vehicle/control APR) both with a SD of 0.55 D and an annual dropout/study treatment discontinuation rate of 7%, a sample size of 217 participants per treatment arm provides an approximate 97% power for the FDA endpoint and an approximate 99.96% power for the EMA endpoint assuming a significant level of 0.025.

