Due to technical issues or non-compliant participants (e.g., wiggly child), not all SE assessments performed may be valid. For PPS sensitivity analysis based on valid SE values, the final average SE (over both eyes) will be calculated only if there is a valid per eye average SE for each eye. A per eye average SE value will be considered valid if there are three non-missing assessments performed for that eye. However, if there are three non-missing SE assessments for a given eye, but one of the SE values differs from the other two SE values for that eye by at least 1 D, only the two SE values that are within 1 D of each other will be considered valid and used to calculate the valid average SE for that eye. Otherwise, all three SE values will be used to calculate the per eye average SE. If there are only two non-missing assessments available for a given eye and the two SE values for that eye are within 0.45 D of each other (i.e., $-0.45 \text{ D} \leq \text{SE Measurement 1} - \text{SE Measurement 2} \leq 0.45 \text{ D}$) then the per eye average SE of those two assessments will be

considered valid. Otherwise, the per eye SE value will be considered invalid for that eye at that visit.

EMA Submission Analysis: Annual Progression Rate

The primary estimand of the primary objective is annual progression rate of myopia. The annual progression rate of myopia for a given timepoint will be calculated as the negative change in SE (average of both eyes) from baseline, divided by the number of days to the timepoint (visit date – date of first dose of study drug + 1), and multiplied by 365.25 days/year. The progression rate will be missing if the SE (average of both eyes) is missing. The multiply imputed average SE (over both eyes) will be used to derive the annual progression rate.

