SYD-101 0.01% and SYD-101 0.03% will be compared to Vehicle for the annual progression rate of myopia after 24 months of treatment using a REML-based MMRM model including fixed effects for treatment group, baseline age category, categorical visit, and the treatment group by visit interaction, with baseline SE value as a covariate. No explicit structure will be assumed for the covariance among the repeated measures. However, in case there is a convergence problem with the unstructured covariance, then a compound symmetry covariance structure will be assumed. The Kenward-Roger Method will be used to calculate the denominator degrees of freedom for the test of fixed effects. All visits for the Month 24 analysis will be included in the model, with the primary comparison at the Month 24 visit.

The above model will be performed for each imputation and the results combined via SAS PROC MIANALYZE for final treatment estimates. The estimated mean annual progression rate of myopia for each treatment at each visit and the estimated mean difference between each SYD-101 treatment group and Vehicle at Month 24 will be presented along with their corresponding 95% CIs.

The analysis described above will be performed for annual progression rate of myopia by eye at Month 24 and repeated for the annual progression rate of myopia at Month 36 with the MMRM model including data for visits through Month 36 as a secondary analysis.

FDA Submission: Confirmed Progression > 0.75 D

Progression is defined as an increased negative change where change is calculated as visit value – baseline value. Progression will be considered missing if a valid SE measurement is not available for both eyes at the given visit. The multiply imputed SE data will be used to determine confirmed progression. For analyses, progression will be considered confirmed if at the next consecutive visit, regardless of the number of days from the prior visit, progression >0.75 D continues to be demonstrated.

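### If the unstructured primary MMRM does not converge, the compound symmetry fallback would overstate the Month 24 standard error of the annualized rate; a heterogeneous-variance fallback costs one sentence

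*SAP*

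**What the plan says.** For the EMA primary endpoint, SAP 8.1.1 (EMA Submission Analysis) defines the annual progression rate as the negative change in spherical equivalent (average of both eyes), "divided by the number of days to the timepoint" and scaled to a year. The rates enter a REML-based MMRM with treatment-by-visit interaction: "All visits for the Month 24 analysis will be included in the model, with the primary comparison at the Month 24 visit".

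On the covariance, the SAP says "No explicit structure will be assumed for the covariance among the repeated measures". The only alternative applies "in case there is a convergence problem with the unstructured covariance", and in that case "then a compound symmetry covariance structure will be assumed". On inference, it says that the "Kenward-Roger Method will be used to calculate the denominator degrees of freedom for the test of fixed effects". No empirical (sandwich) standard error is named. The model is refitted in each of the planned 50 or more imputed datasets and the results are pooled. The SAP does not say whether a convergence failure in one imputation changes the structure for that fit only or for all of them.

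SAP 8.2 repeats the same fallback for change from baseline in axial length. Protocol 9.4.2 is less specific: "An appropriate covariance structure will be selected".

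**The concern.** Dividing a change by time alters its variance from visit to visit. Error in the measured change is multiplied by 1/0.5 = 2 at Month 6 and by 1/2 = 0.5 at Month 24, so early rates should be noisier than late ones. An unstructured covariance absorbs this. Compound symmetry cannot, because it has a single variance for all visits. The Month 24 comparison would then be judged against a standard error that belongs partly to Months 6, 12 and 18. Kenward-Roger adjusts for estimating the covariance parameters; it does not repair a wrong structure.

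At stake are power and an accurate confidence interval for the EMA primary comparison, and for the FDA key secondary endpoint, which uses the same model through Month 36. If convergence failed in only some imputations, results from two different structures could also be pooled.

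**Working it through.** **Inputs from the documents.** 280 per arm, difference 0.18 D/year, SD 0.60 D, two-sided alpha 0.025 (SAP 4.1). Autorefraction is scheduled at Months 6, 12, 18 and 24 through Month 24 (Schedule of Activities; primary-endpoint windows in SAP section 4). An unstructured covariance over four visits has 4 × 5 / 2 = 10 parameters.

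**Assumption.** One visit's averaged spherical equivalent has measurement SD σ of 0.15 to 0.25 D. No SD by visit is given. Protocol section 3 refers to a testing error of about 0.25 D for autorefraction but does not say whether that is an SD.

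**Step 1: reproduce the plan's figure.** SAP 4.1 states that "group sample sizes of 280 per treatment arm achieves >90% power to detect a reduction of 0.18 D or more in the annual progression rate". SE = 0.60 × √(2/280) = 0.0507. Power = Φ(0.18/0.0507 − 2.241) = Φ(1.308) = 90.5%. This agrees.

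**Step 2: variance by visit.** Let Var(rate at t) = s² + 2σ²/t², with t in years and s² set so that the Month 24 SD is 0.60.

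| σ (D) | SD at Months 6 / 12 / 18 / 24 | Month 6 to Month 24 ratio | Mean variance | Pooled SD |
|---|---|---|---|---|
| 0.15 | 0.73 / 0.63 / 0.61 / 0.60 | 1.21 | 0.413 | 0.64 |
| 0.25 | 0.91 / 0.67 / 0.62 / 0.60 | 1.52 | 0.507 | 0.71 |

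**Step 3: reported standard error under compound symmetry.** With nearly complete data and a treatment-by-visit model, the point estimate stays close to the Month 24 mean difference, but its model-based SE uses the mean visit variance. The inflation is k = √(mean variance / Month 24 variance):
- σ = 0.15: k = √(0.413/0.36) = 1.07, SE 0.0543.
- σ = 0.25: k = √(0.507/0.36) = 1.19, SE 0.0602.

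**Step 4: power and type I error.** The true sampling error remains 0.0507; only the reported SE grows. Power is therefore Φ(0.18/0.0507 − k × 2.241), and actual type I error is 2 × [1 − Φ(k × 2.241)].
- σ = 0.15: power 87.5%, type I error 0.016.
- σ = 0.25: power 81.3%, type I error 0.008.

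**Step 5: wider range.** Other assumed variance models give Month 6 to Month 24 SD ratios from 1.08 (noise of SD 0.125 D in the change) to 2.00 (progression in independent increments). Inflation then runs from 1.025 to 1.443 and power from 89.5% to 62.3%. REML compound symmetry fits to simulated trials (25 per scenario) confirm the SE: 0.0555 against 0.0505 from Month 24 alone with change noise of 0.25 D, and 0.0732 against 0.0506 with independent increments. Point estimates differed by at most 0.006 D/year.

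**Step 6: the SAP's expected effect.** SAP 4.1 takes 0.65 against 0.325 D/year, SD 0.55, 217 per arm and 7% annual dropout, which leaves 217 × 0.93² ≈ 188 per arm. Power is 99.98% without the problem and between 99.97% and 99.4% with it, over the range in Step 5.

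**Step 7: axial length.** This outcome is raw change, not a rate, and biometry is annual, so the Month 24 model has Months 12 and 24 only. If variance grows in proportion to t (assumption), the SE ratio is √[((1 + 2)/2)/2] = 0.87. If it grows with t² (assumption), the ratio is √[((1 + 4)/2)/4] = 0.79. A nominal two-sided 5% test would then have actual error of about 9% or 12%.

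**The case against.** The strongest objection is that this concerns a fallback that will probably never run. Ten covariance parameters, about 840 children and data largely completed by imputation make non-convergence unlikely; for axial length through Month 24 there are only three parameters. That stands, and it keeps the severity low. It is also fair that each analysed value averages three readings per eye and then both eyes, so the noise could sit at or below the low end of the range, where the loss is 1 to 3 points.

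Three stronger readings are tempting, and the documents do not support them:

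- A reader might infer that the primary p-value could be falsely significant. On these assumptions the SE is too large, the type I error falls below nominal and the estimate barely moves.
- A reader might put the pooled SD into the sample-size formula and conclude that power falls to 86% to 77%. That treats the estimate as truly more variable, when only its reported SE is inflated.
- A reader might extend the mixing of structures to the fast-progressor subsets. SAP 3.3 and 8.2 rule out multiple imputation there, so there are no imputations to mix.

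None of this defends compound symmetry as the only alternative for a time-divided outcome. Nor does it answer the SAP's silence on keeping one structure across imputations.

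**Conclusion.** The point holds as a free improvement of low severity. If the fallback were triggered, the reported Month 24 SE for the annualized rate would be too large: by about 7% to 19% for a measurement SD of 0.15 to 0.25 D, which costs about 3 to 9 points of power at 0.18 D/year and less than 1 point at 0.325 D/year. The size rests on assumed noise and on nearly complete data. It would be greater if each child's progression varies over time. EMA observations after escape or prohibited treatment are censored without imputation, so a wrong structure could also shift the estimate there; this was not quantified.

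For axial length the mechanism differs and the direction probably reverses. If variance grows with follow-up, the Month 24 SE would be too small. That is the less safe direction, though it concerns the last endpoint in the testing order and an even less likely trigger.

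**What to change.** In SAP 8.1.1 and 8.2, replace the compound symmetry sentence with an ordered list of structures that let the variance differ by visit, for example heterogeneous Toeplitz, then heterogeneous first-order autoregressive, then heterogeneous compound symmetry. Keep plain compound symmetry only as the last resort, with an empirical (sandwich) SE and a stated degrees-of-freedom method, since Kenward-Roger rests on the model-based covariance.

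For the imputed analyses, add that the first structure to converge in all imputations is used for every imputation. Align Protocol 9.4.2 with this by referring to the SAP.

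The cost is one or two SAP sentences. The estimand, the planned unstructured analysis and the data collected do not change. It is free only if made before unmasking at Month 24; the documents do not give that lock date. After it, the change should be recorded as made post-unmasking for Month 24 and as prospective for Month 36 only if those data are still masked.

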Treatment Discontinuation	
EMA Endpoint: Hypothetical
 
 • Observations after DC due to a related AE will be multiply imputed assuming missing not at random (MNAR) using a sequential vehicle-based pattern regression • Observations after Treatment DC for other reasons will be multiply imputed assuming MAR 
FDA Endpoint: Composite
 
 • Participants with discontinuation (DC) due to a related AE are non-responders • Observations after Treatment DC for other reasons will be multiply imputed assuming MAR 	
Discontinuation due to related AE are labelled non-responders is a conservative strategy as the discontinuation is related to treatment. Other reasons for discontinuation will be considered to occur at random.
 
Treatment policy will be used as a sensitivity analysis as this will reflect real world use including potential rebound effect when participants discontinue treatment.

Study Discontinuation	
EMA Endpoint: Hypothetical
 
 • Observations after DC due to a related AE will be multiply imputed assuming missing not at random (MNAR) using a sequential vehicle-based pattern regression • Observations after Treatment DC for other reasons will be multiply imputed assuming MAR 
FDA Endpoint: Composite
 
 • Participants with discontinuation (DC) due to a related AE are non-responders • Observations after Treatment DC for other reasons will be multiply imputed assuming MAR 	
This study was enrolling, and a large portion of participant follow-up was during the ongoing COVID-19 pandemic. The majority of study discontinuations are logistical due to withdrawal of consent.
 
Discontinuation due to related AE are labelled non-responders and is a conservative strategy as the discontinuation is related to treatment. Other reasons for discontinuation will be considered to occur at random.

Invalid SE Values	
Treatment Policy
 
 • Invalid SE values will be used 	Given the age of children as participants, in clinical practice it would be expected to have non-ideal auto-refraction assessments

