8.1.1. Primary Analysis

Calculation of SE:

The primary efficacy endpoints for EMA and FDA are based SE. SE values will be calculated for each autorefraction for each eye as the sum of the sphere power with half of the cylinder power (SE = sphere + $\frac{1}{2}$ cylinder). The SE for each measurement will be calculated for each eye and then averaged by eye; the participant's averaged right eye SE and averaged left eye SE will then be averaged (i.e., a single averaged SE value for a given visit will be obtained for each participant by taking the “average of the averages”).

Per protocol, the autorefraction procedure is to be performed 3 times in each eye. If there are less than three measurements for a given eye, the available SE values will be averaged for that eye prior to averaging the right and left per eye SE averages for the final average SE (over both eyes) value for analysis. This final per participant average of SE from the right and left eyes will be used for analysis.

The final average SE (over both eyes) will be considered missing if a non-missing SE measurement is not available for both eyes at a given visit. For a given eye, SE is considered non-missing if there is at least one measurement with a non-missing sphere and a non-missing cylinder value recorded for the same autorefraction measurement. If the baseline final average SE (over both eyes) is missing from the autorefraction, the SE assessment result from the manual refraction will be used.

Data imputations:

A combination of hypothetical, composite, and treatment policy strategies for intercurrent events will be used for the primary estimands as detailed in Section 3.2. For the EMA and FDA, intermittent missing data or observations post study or treatment discontinuation not due to a related AE, will be multiply imputed using via Markov Chain Monte Carlo (MCMC) methods assuming the missing data is MAR (Missing at Random). However, for by eye analysis data will be analyzed as observed.

For the EMA, observations after specified prohibited or escape treatment will be observed until day of prohibited or escape treatment; observations following prohibited or escape treatment will be censored and not imputed. For the FDA primary estimand, observations post prohibited or escape treatment will be considered non-responders.

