For the EMA primary estimand, observations post study or treatment discontinuation due to a related AE will be multiply imputed assuming missing data is MNAR (Missing Not at Random). For the FDA primary estimand, observations post study or treatment discontinuation due to a related AE will be considered non-responders.

For the EMA and FDA, observations with invalid SE values will be analyzed as observed.

For any imputations, the value to be imputed is the average SE value (average of both eyes). This same set of imputed SE values will be used to calculate the primary efficacy endpoints for EMA and FDA, as well as the key secondary and applicable secondary efficacy endpoints derived from SE. All imputations will be based on set SEEDS. It is planned to perform k=50 imputations, however the number of imputations may be increased depending on the amount of missing data.

MAR imputations will be performed separately for each treatment arm and the imputation model will include terms for age at baseline, baseline SE (average of both eyes), and SE values (average of both eyes) for each post baseline scheduled visit through the specified analysis timepoint, Month 24 or Month 36 as applicable.

Imputations for data assumed to be MNAR will be first imputed via MCMC multichain methods to obtain monotone data as above for MAR imputations. The remaining missing SE values will be imputed via a sequential vehicle-based pattern imputation using regression methods ([Ratitch, 2011](#)) for the scheduled SE visits through the analysis timepoint, Month 24 or Month 36, using a model including age at baseline and baseline SE (average of both eyes) followed by sequential visits through M24 or M36, imputed values for those on SYD-101 treatment will be based on the Vehicle group.

Data sets will be sorted by treatment and participant id prior to imputation.

Valid SE Values:

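### SAP 8.1.1 makes FDA progression missing without a *valid* SE in both eyes, which conflicts with the rule that invalid SE is analysed as observed

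*SAP*

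**What the plan says.** Four parts of the plan bear on this point.

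- **When SE is missing.** SAP 8.1.1, Calculation of SE, sets the rule visit by visit: "The final average SE (over both eyes) will be considered missing if a non-missing SE measurement is not available for both eyes at a given" […]. It adds: "For a given eye, SE is considered non-missing if there is at least one measurement with a non-missing sphere and a non-missing cylinder value". One complete reading per eye is therefore enough.
- **How invalid SE is handled in the primary analysis.** SAP 8.1.1, Data imputations: "For the EMA and FDA, observations with invalid SE values will be analyzed as observed". SAP Table 3-2 gives the strategy as treatment policy: "Invalid SE values will be used". The primary row of SAP Appendix 14.1, protocol Table 9-2 and protocol 9.4.2 agree.
- **What *valid* means.** SAP 8.1.1, Valid SE Values, opens: "For PPS sensitivity analysis based on valid SE values, the final average SE (over both eyes) will be calculated only if" each eye has a valid average. It continues: "A per eye average SE value will be considered valid if there are three non-missing assessments performed for that eye". Two readings are valid if they lie within 0.45 D of each other. The rule closes: "Otherwise, the per eye SE value will be considered invalid for that eye at that visit".
- **How FDA progression is derived.** SAP 8.1.1, FDA Submission: "Progression will be considered missing if a valid SE measurement is not available for both eyes at the given visit". The next sentence takes confirmed progression from the multiply imputed SE data.

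The corresponding EMA paragraph makes the progression rate missing only when average SE is missing. The FDA paragraph in protocol 9.4.2 carries no validity condition.

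**The concern.** The FDA sentence uses a word that the same section has just defined, and with that definition it contradicts the estimand. A visit with a usable but invalid SE is to be analysed as observed under Table 3-2, and is to have missing progression under the endpoint derivation. Both cannot be applied to the same visit.

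At stake is whether observed refractions count towards the FDA primary endpoint. Confirmation requires progression above 0.75 D at the next consecutive visit, so losing a visit can remove a crossing or the visit that confirms it. If the next usable visit then serves as the confirming one, it can also skip a visit that would have failed to confirm.

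The conflict extends beyond the FDA primary endpoint. SAP 8.1.1 runs the same analysis at Month 24, and protocol 9.4.3 assigns that method to the EMA key secondary endpoint, for which Table 3-4 also says that invalid values are used. SAP 8.1.2 repeats the 8.1.1 analysis for the sensitivity approaches, and Sensitivity Analyses 2 to 6 likewise analyse invalid SE as observed.

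**Working it through.** The plan gives no figure on this point, so the check compares the rules and applies them to example readings.

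**Step 1: the two rules for one eye.**
- Non-missing (Calculation of SE): number of complete readings ≥ 1.
- Valid (Valid SE Values): three readings, or two readings with |reading 1 − reading 2| ≤ 0.45 D. Otherwise invalid.

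**Step 2: illustrative readings in one eye, with the other eye assumed to have three good readings.**

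| Readings (D) | Check | Non-missing? | Valid? | Table 3-2 and imputation text | FDA sentence read literally |
|---|---|---|---|---|---|
| −2.0 | 1 reading | yes | no | SE used | progression missing |
| −2.0, −2.5 | difference 0.50 > 0.45 | yes | no | SE used | progression missing |
| −2.0, −2.4 | difference 0.40 ≤ 0.45 | yes | yes | SE used | SE used |
| −2.0, −2.1, −2.2 | 3 readings | yes | yes | SE used | SE used |

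The rules diverge in exactly two situations: one reading in an eye, or two readings more than 0.45 D apart. The SAP expects such visits. Its validity paragraph refers to technical problems and uncooperative children, and section 5.2 lists a single autorefraction per eye as a possible major deviation.

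**Step 3: what would happen to such a visit.** SAP 8.1.1 says that the imputed quantity is average SE and that one imputed set serves both agencies' endpoints. An invalid SE is not missing under Calculation of SE, so it would not be imputed in that set. On the literal reading, progression would be missing with no stated rule to fill it, or the FDA endpoint would need its own imputed set, contrary to the shared-set statement. The text does not settle which.

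**Step 4: where invalid SE is deliberately set aside.** SAP 8.1.2 and Appendix 14.1 impute it under missing at random in Sensitivity Analysis 1, on the per-protocol set. Excluding it from the primary analysis as well would weaken one of the contrasts that analysis is meant to provide. It would also let a sensitivity-analysis tolerance affect the primary endpoint, and that tolerance is 0.45 D in the SAP but 0.25 D in protocol 9.1.1.

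**Step 5: planning figures.** For 280 per arm, a 15-point difference and two-sided alpha 0.025, the lowest power over all vehicle rates is 90.7% (at vehicle rates of 57% to 58%). The stated minimum of 90% reproduces. It does not depend on the wording at issue.

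**The case against.** The strongest reply is that the intent is already clear. Both documents say repeatedly that invalid SE is used in the primary analysis, once within section 8.1.1 itself and explicitly for both agencies. The validity definition is confined to the per-protocol sensitivity analysis. The FDA sentence is also built almost exactly like the missing-SE sentence under Calculation of SE, with *valid* in place of *non-missing*, and it speaks of an SE measurement, whereas the validity rule concerns a per-eye average. One adjective should not override the estimand.

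Most of this stands: loose drafting is the likely explanation. It does not remove the conflict, because the sentence is the operative derivation rule for a primary endpoint, the SAP nowhere says that *valid* has a different meaning there, and someone programming from that paragraph could reasonably apply the definition given just before it.

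Two stronger readings are tempting, and the documents support neither. A reader might infer that the affected visits would be imputed in the FDA primary analysis; as Step 3 shows, that does not follow. A reader might also assume a per-visit invalid rate and compound it over the six scheduled post-baseline autorefraction visits to Month 36. The documents give no such rate. Compounding also assumes that visits are independent, whereas an uncooperative child is likely to give repeated poor readings. And the result would count participants with an affected visit, not changed outcomes, since confirmed progression at any time up to Month 36 may be unaltered by one visit.

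**Conclusion.** The inconsistency is real, and it lies in the rule that derives the FDA primary endpoint. It is confined to visits where an eye has one reading or two readings more than 0.45 D apart. At those visits the sentence, taken with the SAP's own definition, sets progression to missing although SE was observed, against the stated estimand and without a clear rule for what follows. The EMA key secondary endpoint at Month 24 shares the problem.

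Its numerical size cannot be determined from the documents, and neither can its direction, since a lost visit can remove a confirmed event or skip a visit that would have failed to confirm. A figure for lost power would have to assume both how often such visits occur and that the participants concerned contribute nothing, and the documents support neither.

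The conclusion rests on reading *valid* as the SAP defines it. If it means *non-missing*, the intended analysis is sound and only the wording is at fault. The correction should still be made, because the sentence governs a primary endpoint.

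**What to change.** In SAP 8.1.1, FDA Submission, replace the condition so that progression is missing when the average SE (over both eyes) is missing, as defined under Calculation of SE. Add one sentence stating that the valid-SE rule applies only to the per-protocol sensitivity analysis (Sensitivity Analysis 1).

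This agrees with the estimand tables, the imputation text and Appendix 14.1 in the SAP, and with Table 9-2 and section 9.4.2 of the protocol. It costs one phrase and one sentence in the SAP, plus a check that the progression-derivation program tests for missing rather than invalid SE. No protocol text, sample size, alpha or model changes.
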